Primary objective: To evaluate the feasibility (study design, methods, processes) and acceptability (family/child/clinician satisfaction, perceived usefulness) of conducting a RCT of a novel, brief, coaching intervention (SFC-Peds) for improving and sustaining PA and dietary habits in CWPD.

Secondary objective: To determine the responsiveness of selected outcome measures to SFC-Peds coaching over 12 months.

Principal research question: *“Is an efficacy trial to evaluate a six month SFC-Peds intervention to improve PA and dietary habits feasible to implement and acceptable to CWPD and families?”*

APPROACHES AND METHODS

Design: We will use a pilot RCT design [82] with two groups: One group (n=15) will work with a coach trained in SFC-Peds eight times over six months. The other group, the control group (n=15), will receive only standard printed materials at the start of the study. These materials will also be available to the SFC-Peds group to control for bias on study measures. The control group will allow us to control for information, maturation, repeated testing and attrition over the 12 month study [83]. All participants will receive standard care from existing clinicians who will not be delivering the SFC-Peds study intervention. The *feasibility* of trial processes, management, and resources will be assessed quantitatively. The *acceptability* of trial participation and coaching processes will be explored qualitatively. Qualitative enquiry lends insight into potential mechanisms of change and barriers to implementation and is therefore highly recommended when evaluating complex interventions [34].

Sample: Thirty children aged 10–18 inclusive and their parents who live within approximately two hours of Holland Bloorview Kids Rehabilitation Hospital (Toronto, ON) up to Thames Valley Children’s Centre (TVCC) (London, ON) will participate. The sites serve diverse socio-cultural communities.

Children and Teens in Charge of their Health: A feasibility study of solution-focused coaching to foster healthy lifestyles in children and young people with physical disabilities.

Child inclusion criteria:

- i) Between the age of 10 – 18 years inclusive
- ii) Diagnosis of SB or CP
- iii) Has physical capability to execute independent body movement with or without device
- iv) Cognitively able and willing to set PA or dietary goals
- v) Can communicate in English and respond to questions requiring some reflection and insight
- vi) Home internet connection

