All participants will receive standard care throughout. This may vary with the child's age, diagnosis, functional level and co-morbidities. Our previous work shows that advice related to PA/diet is rarely given with standard care [89]. However, to document any potential co-interventions, all interactions between study participants and their service providers will be recorded on a standard form (see Appendix 6). The study will thus identify any differences in standard care between groups and across sites, and will inform recruitment, stratification and data analysis in the full RCT. We will identify if any service providers have SFC-Peds training. Coaches will not be part of participants' standard care.

Control information

After randomization, all participants will be given basic printed information relating to PA and healthy diets based upon Health Canada's *Eat Well and Be Active Toolkit* (www.health.gc.ca/eatwell-beactive), which has been reviewed for suitability by expert team members (*[name], [name], [name]*). This ensures that all children have exposure to information on healthy habits, thereby meeting our ethical imperative and ensuring a scientifically rigorous control group. It also helps to control for bias of responses on outcome measures (see Appendix 7 for booklet).

Intervention training

Coaches will be clinicians with physiotherapy, kinesiology, therapeutic recreation, dietetics or similar training who have already been trained in SFC-Peds. They will undertake a half day of training from expert team members, including Canadian PA and diet guidelines [90, 91], and their application to children with SB and CP (*[name], [name], [name]*).

Intervention implementation

Children and Teens in Charge of their Health: A feasibility study of solution-focused coaching to foster healthy lifestyles in children and young people with physical disabilities.

Children randomized into the SFC-Peds group ($n=15$) and their parents will be allocated a coach for eight 60-min SFC-Peds sessions over six months. A six month intervention is supported by meta-analyses of health promotion studies for typically developing children [92] and adults [93]. Time is allowed between sessions for children and parents to work on their goals [27, 70] (see Appendix 11 for coaching schedule).

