Intervention Measure of Engagement – Service Provider (PRIME-SP) (see Appendix 11) and will be assessed by the coaches after each coaching session [126].

STUDY OUTCOMES AND PROCEDURES

Study Procedures

After enrollment into the study, participants will complete the following assessments at the time points outlined below (see Appendix 12 for assessment schedule). Children in the SFC-Peds group will receive the eight 60 minute coaching sessions between Time 1 and Time 2.

Assessment Timings

To assess participant retention, the feasibility study will use four assessment points over 12 months as in the planned efficacy trial: **Time 1 Baseline** (immediately preceding randomization); **Time 2** (immediately post-intervention or 6 months post-baseline for control group +/- 2 weeks); **Time 3** (three months post-intervention or 9 months post-baseline for control group +/- 2 weeks); **Time 4** (6 months post-intervention or 12 months post-baseline for control group +/-4 weeks).

Study Assessments

PRIMARY OBJECTIVE: *To evaluate the feasibility and acceptability of conducting a RCT of a novel, brief, coaching intervention (SFC-Peds) for improving and sustaining PA and dietary habits in CWPD.*

Trial feasibility will be assessed using the following pre-identified criteria (as recommended [82]):

Recruitment	2–3 participants/month recruited over 12 months (for target sample size $n=30$)	$\geq 10\%$ recruitment response rate achieved (min. feasible RCT response rate [99])
Attrition	85% participants successfully complete study (i.e. complete T1 & T4 evaluations)	75% participants complete all assessments (i.e. protocol adherence)
Adherence	Successful completers participate in $\geq 75\%$	75% of the participants complete

Children and Teens in Charge of their Health: A feasibility study of solution-focused coaching to foster healthy lifestyles in children and young people with physical disabilities.

	meetings with coach	evaluations in ≤ 2 hrs (to assess burden)
Stratification	Intervention/control groups similar for age and gender	Intervention/control groups comparable on diagnosis and functional mobility
Fidelity	High intervention fidelity (>8/10 on the Solution-Focused Fidelity Instrument [98])	Challenges/ease of remote coaching (coach, child, family report)

Trial acceptability will be explored qualitatively:

Semi-Structured Survey

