Time 4 (SFC-Peds group): Children and their parents in the SFC-Peds group will undertake separate in-depth interviews facilitated by a qualitative interviewer to explore their experiences after coaching completion, perceived impact of intervention, barriers/facilitators to maintaining PA and dietary habits, and any unmet needs (see Appendix 16 for interview guide). Children will be asked to select 6-8 of their photographs taken since Time 2 to share with the interviewer. This will help remind children of their lifestyles in the previous six months, and enable them to speak in more depth about their feelings and experiences [106]. Each child will first be asked to explain why he/she took the photo, its meaning, what it shows of his/her coaching experience and the time since it ended.

Survey Time 4 (Control group only)

Time 4 (Control group): Children in the control group ($n=15$) will complete a Time 4 survey (see Appendix 17) regarding what they liked most/least about the study, any changes in health habits in the previous 12 months, acceptability of not getting the intervention, and tolerance of assessment protocols [30].

Qualitative Interview (Coaches only)

Time 4 (Coaches): Coaches will be interviewed to explore their experiences of delivering the intervention, e.g. challenges/facilitators, optimal coaching doses, use of technology (see Appendix 18).

Children and Teens in Charge of their Health: A feasibility study of solution-focused coaching to foster healthy lifestyles in children and young people with physical disabilities.

SECONDARY OBJECTIVE: *To determine the responsiveness of outcome measures to SFC-Peds coaching over 12 months.*

The following measures (excluding gender and date of birth) will be administered at Times 1, 2, 3, and 4 for all participants (approximately 1.5 hours duration). Issue identification and goal attainment measures are administered to SFC-Peds participants only with the first assessment conducted during the first coaching session. Measures have been selected based upon evidence of their responsiveness to change and psychometric properties in previous health promotion interventions [18]. Parent and child report questionnaires may be completed at home or online if the family prefers.

Participant characteristics

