SECONDARY OBJECTIVE: Measure responsiveness will be established by pre-post intervention differences using effect sizes (Cohen's *d*) and confidence intervals both within and between groups. It is well accepted to examine mean score changes for clinically significant differences pre and post intervention without calculating statistical significance (e.g. a score change of at least 2 points on the COPM is considered clinically significant [38]). We will therefore be able to assess the potential value of SFC-Peds over receiving printed materials only by examining goal scores over time. Our secondary outcomes will be compared with objective behaviour change (goal attainment) for concordance (e.g. whether successful goal attainment corresponds with increased self-determination). We will examine differences in outcome measures by disability, functional mobility, gender and age.

CHALLENGES

Our intervention (SFC-Peds) is largely virtual to reduce burden and enhance adherence [43]. All participants will receive gift cards for completing assessments to reduce attrition; this is a key feasibility outcome, especially in the control group. To reduce possible biases, participants will not meet during the study and coaches will not be involved in standard care. Standardized training (by 3 certified coaches) will be provided. Assessors will be asked which group they think participants are in; blinding success is indicated by accuracies at or below chance level. If adaptations are needed for the RCT, 'A process for Decision making after Pilot and feasibility Trials' (ADePT) [124] will be followed.

KNOWLEDGE TRANSLATION (KT)

A KT planning template [40] will ensure our findings have maximum reach yet are appropriate for feasibility study outcomes. The plan capitalizes on close collaboration of knowledge users and researchers within our investigative team. Integrated KT is promoted throughout the project by the involvement of clinical, family and knowledge user stakeholders, to ensure that the outputs meet the needs of the end users [125]. Holland Bloorview Research Family Engagement Committee members

Children and Teens in Charge of their Health: A feasibility study of solution-focused coaching to foster healthy lifestyles in children and young people with physical disabilities.

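### Within-group Time 1 to Time 2 change cannot separate coaching from season or other time effects; responsiveness at Time 2 should rest on the difference from control, and goal scores have no control values

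*Combined protocol and SAP*

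**What the plan says.** - **Analysis.** Under Data Analyses, secondary objective, "Measure responsiveness will be established by pre-post intervention differences", expressed as Cohen's d with "confidence intervals both within and between groups". The sentence does not name the pre and post visits. The same paragraph expects goal scores over time to show what coaching adds to the printed information.
- **Objective.** "To determine the responsiveness of selected outcome measures to SFC-Peds coaching over 12 months".
- **Timing.** Coaching is "eight 60-min SFC-Peds sessions over six months" (Intervention implementation). Under Assessment Timings, Time 2 is "immediately post-intervention or 6 months post-baseline for control group +/- 2 weeks" and Time 4 is "6 months post-intervention or 12 months post-baseline for control group +/-4 weeks".
- **Measures.** Apart from gender and date of birth, the measures "will be administered at Times 1, 2, 3, and 4 for all participants". Activity and diet are listed among the secondary outcomes, which are introduced as between-group comparisons. GAS and COPM are given to the coached arm only, first at the first coaching session.
- **Recruitment.** The feasibility criterion is 2–3 "participants/month recruited over 12 months" for 30 children.
- **Season.** It is not mentioned in the text available: not among the influences the control group is meant to handle (Design), not as a stratum (Randomization), and not among the factors examined in the analysis.

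**The concern.** Activity, and diet recalled over the past 30 days, describe the period around the visit. Two visits half a year apart compare different parts of the year, so a single-arm change contains a seasonal component as well as any coaching effect, maturation and repeated testing. If that change is read as responsiveness to coaching, a measure could look responsive, or unresponsive, partly because of when children enrolled. The outcome set for the full trial could then be chosen on a misleading figure.

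The problem is sharper for GAS and COPM, which are headed as the primary outcome measure. The Design section justifies the control group as a guard against maturation and repeated testing, but that group supplies no goal scores. Nothing can therefore be subtracted from the coached arm's goal change, whether the competing cause is season or another time effect.

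**Working it through.** **The plan's own figure.** The plan gives no number on this point. Its only stated effect size, 0.55 with power 0.80 and n = 15, concerns GAS. It reproduces with one-sided alpha 0.10: ((1.2816 + 0.8416)/0.55)² = 14.90, so 15. It is not a yardstick for activity or diet.

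**Assumptions.** Season follows a 12-month cosine, s(t) = A cos(2πt/12). A is 0.1 to 0.3 SD of the measure (peak to trough 0.2 to 0.6 SD). With pre-post correlation 0.5, the variance of change is 2(1 − 0.5) = 1, so the same SD unit applies to change scores.

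**One child.** Six months after enrolment at phase θ, the seasonal change is −2A cos θ. It ranges from −2A to +2A with enrolment date, is near zero midway between the extremes, and is below A in size for one third of dates.

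**Arm mean, steady enrolment over W months.** The largest possible mean shift, over all starting dates, is 2A × |sin(πW/12)| / (πW/12).

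| Enrolment | Shift | For A = 0.1 to 0.3 |
|---|---|---|
| 12 months, even | 0 | 0 |
| 10 months (30 children at 3 per month) | 0.38A | 0.04 to 0.11 SD |
| 15 months (30 children at 2 per month) | 0.36A | 0.04 to 0.11 SD |

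**Half of an arm in one quarter centred on an extreme.**
- The mean over that quarter is 2A × sin(π/4)/(π/4) = 1.80A.
- The other half is spread over the remaining nine months. Their mean is −1.80A × 0.25/0.75 = −0.60A, because the full year averages zero.
- The arm mean is 0.5 × 1.80A − 0.5 × 0.60A = 0.60A, or 0.06 to 0.18 SD.
- If both arms behave this way, 15 of 30 children enrol in three months, or 5 per month. The plan's 2–3 per month gives 6 to 9 per quarter (20% to 30%).

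**Noise with even enrolment.** Season adds 2A² = 0.02 to 0.18 to a change variance of 1. The SD, and so the interval width, grows by a factor √1.02 to √1.18 = 1.01 to 1.09.

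**Between-group difference.** In simulated random 15/15 splits, the expected seasonal bias is zero in every enrolment pattern tried. With even enrolment, chance imbalance has SD 0.53A (0.05 to 0.16 SD). This is the same noise as in the line above, not an addition to it.

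**Time 1 to Time 4.** The seasonal change is zero at exactly 12 months. At the edge of the four-week window (0.92 month) it is at most 2A sin(π × 0.92/12) = 0.48A for one child.

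**Scale.** With 15 per arm, the standard error of a mean change is 1/√15 = 0.26 SD within an arm and √(2/15) = 0.37 SD for the difference. The largest shift at planned recruitment rates, 0.11 SD, is under half of the within-arm standard error.

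**The case against.** The strongest reply is that the plan already holds most of the remedy. Activity and diet are introduced as between-group comparisons, between-group effect sizes with intervals are planned, and Time 4 data are collected in both arms in about the same season as Time 1. All of that stands. What remains is that the within-group effect size is given equal standing as a basis for responsiveness, and that goal scores have no control values.

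Several stronger readings are tempting, and the documents do not support them:
- **Every child is re-measured in the opposite season, so the whole arm shifts one way.** The sign of the shift depends on enrolment date. With even enrolment over 12 months the shifts cancel in expectation.
- **Pre-post means Time 1 to Time 2 only.** That is the natural reading, since Time 2 is labelled as immediately after the intervention. The analysis section does not say it, and the objective covers 12 months.
- **Half of an arm in one quarter shifts the mean by half of 1.80A.** This treats the other half as averaging zero. They occupy the remaining nine months and pull the other way, giving 0.60A.
- **The arm comparison is biased by season.** It is not, in expectation, provided coaching keeps to its six months so that both arms reach Time 2 after the same interval.

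It is also fair to say that no feasibility criterion depends on this, and that the missing control values for GAS and COPM are a wider matter than season.

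**Conclusion.** The point holds as a minor one. A within-group Time 1 to Time 2 change in activity or diet cannot by itself distinguish coaching from season or other time effects, and the plan lets it serve as a basis for responsiveness. The within-arm shift is zero in expectation with even enrolment over 12 months, at most 0.04 to 0.11 SD at the planned rates, and 0.06 to 0.18 SD if half of an arm enrols in one extreme quarter. All of these rest on an assumed amplitude of 0.1 to 0.3 SD, a cosine season and pre-post correlation 0.5; none comes from the documents.

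The conclusion about goal scores needs no seasonal assumption. GAS and COPM exist only in the coached arm, so their change over time cannot show an advantage over printed materials.

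**What to change.** In the secondary-objective paragraph of Data Analyses:
1. Name the pre and post visits.
2. For activity and diet, rest the responsiveness conclusion at Time 2 on the between-group effect size and its interval. Show within-group Time 1 to Time 2 change, and the same-season Time 1 to Time 4 change, as descriptive support.
3. Report enrolment month by arm, so that a reader can see whether enrolment clustered.
4. State that GAS and COPM change is uncontrolled, is not evidence of benefit over printed materials, and is not attributed to coaching alone.

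A season covariate is not worth adding: the plan contains no regression model and has 30 children. Splitting goal scores by season would leave about 7 against 8 children.

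**Cost.** Wording only, with no new visits or measures. Enrolment and visit dates are implied by the visit windows, though the text does not state that they are recorded. The within-group effect sizes carry less weight. The between-group interval is wider, by a factor of about √2 = 1.41 with 15 per arm and equal change SDs. Time 4 also reflects any fading after coaching, so it supports the Time 2 result without replacing it.

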- vii) Lives within 2 hours driving distance from Toronto up to London, Ontario OR willing to travel to either HB or TVCC for first in-person coaching session if randomized into coaching group

Child exclusion criteria:

- i) Surgery in past 6 months or upcoming 12 months that may impact PA or dietary intake (e.g. orthopedic surgery or neurosurgery)
- ii) Medical condition severely restricting diet
- iii) Underweight (less than fifth percentile)
- iv) Receiving specialist dietetic services

Parent inclusion criteria:

- i) Primary caregiver to a study participant
- viii) Can communicate in English and respond to questions requiring some reflection and insight

Sample size

Feasibility studies do not assess intervention efficacy and therefore do not require formal sample size calculations [33, 85]. The sample size ($n=30$) was set as a minimum needed to assess the key feasibility issues, as per feasibility best practices [86]. Fifteen SFC-Peds participants will suffice to show

Children and Teens in Charge of their Health: A feasibility study of solution-focused coaching to foster healthy lifestyles in children and young people with physical disabilities.

a tendency ($p < 0.10$) within the intervention group of behavioural change assessed by Goal Attainment Scaling (GAS; see ‘Outcomes’), equal to an effect size of 0.55 with a power of 0.80. The responsiveness of the secondary outcome measures will be compared with goal scores for evidence of concordance, e.g. a tendency of correlation between behavioural change and the Arc’s Self-Determination Scale. *Post hoc* estimates of variance will be key for the full trial’s design as they will inform the power calculations of the eventual RCT [85]. The sample size will allow us to assess recruitment success and show whether testing procedures, coaching goals and follow-up sessions are consistent across groups, mobility levels and sites. This sample size will also provide sufficient data for the qualitative work we are proposing to explore acceptability [87, 88].

Recruitment

We will recruit 15 children with SB and 15 children with CP (a total of 30 participants) and their parents from Holland Bloorview and TVCC.

Recruitment at Holland Bloorview

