At this session, the RC will clarify any concerns, and answer any questions clients or parents might have and will judge the child's capacity to provide informed consent, guided by a structured tool (see Appendix 3). If the RC judges the child to have answered questions about the study with reasonable understanding, the child will sign the Informed Consent Form (ICF) (see Appendix 4). Otherwise, a parent will sign the ICF and the child will provide their assent (see Appendix 5). For parents who are willing to participate in the interviews and parent measures the parent will sign the ICF for their own participation in the study. The RC obtaining informed assent from prospective participants (children) will familiarize the potential participant about assent by explaining what free, informed consent is and how research is different from clinical care. The RC will have an open and age appropriate discussion with each child to assess readiness for assent. The RC may consult the parent to identify accommodations to assist in decisions to participate. The assent and consent forms will be provided prior to this discussion in order for families to review them on their own. While meeting with the client and parent, the RC will clarify any concerns, and answer any questions clients or parents might have. During this process, the highly experienced RC will observe and listen for any verbal and nonverbal indications of dissent. Furthermore, the RC will ensure ongoing informed assent by reconfirming agreement to participate throughout the study. At the end of the study, the family will receive a study summary letter at the end of the study. The local REB fully endorses these processes.

Randomization

Once participants have provided written informed consent and completed all baseline measures, they will be randomized into the study. The PLAN procedure of SAS/STAT software will create a random sequence to test randomization. Randomization block size will not be known to research staff to ensure blinding. Group allocation occurs after baseline assessment, stratified by diagnosis and recruitment site.

Children and Teens in Charge of their Health: A feasibility study of solution-focused coaching to foster healthy lifestyles in children and young people with physical disabilities.

Standard care

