DEMOGRAPHICS: Gender, date of birth, ethnicity, diagnoses, medications, current sports involvement (see Appendix 19 for demographics form). Questions from the International Study of Childhood Obesity, Lifestyle and the Environment survey (see Appendix 20) about the child's environment (e.g. accessibility of play areas) will also be collected [107].

FUNCTIONAL MOBILITY: The six-minute walk test for walkers [108] and the six-minute push test for non-walkers [109] (see Appendix 21).

Primary outcome measure

ISSUE IDENTIFICATION AND GOAL ATTAINMENT (CHILD REPORT):

Within-group change will be assessed using the Canadian Occupational Performance Measure (COPM) (see Appendix 22), which identifies the person-centred goal performance issues to improve, and assesses changes in occupational performance and satisfaction. Participant goal attainment will be assessed using Goal Attainment Scaling (GAS) (see Appendix 23), by defining five levels of goal attainment, thus ensuring that all attainment levels are mutually exclusive and measurable. This is an

Children and Teens in Charge of their Health: A feasibility study of solution-focused coaching to foster healthy lifestyles in children and young people with physical disabilities.

objective measure of behaviour change [110]. To minimize bias, GAS and COPM re-assessment will be conducted by a coach who has not worked with the child.

Secondary outcomes measures:

Between group change will be examined using the following measures:

BEHAVIOURAL ASSESSMENTS (CHILD REPORT):

Physical activity: The Habitual Activity Estimation Scale [111] (see Appendix 24) estimates time spent inactive, somewhat inactive, somewhat active, and very active, and shows good correlation with moderate to vigorous PA measured by accelerometry in our population ($p=0.02$) [112, 113].

Diet: The Dietary Screener Questionnaire (see Appendix 25) assesses dietary intake over the past 30 days and is validated against 24 hour multiple recall [114].

PSYCHOSOCIAL ASSESSMENTS (CHILD REPORT):

Self-determination: The *Arc's Self-Determination Scale* (see Appendix 26) has excellent reliability/validity with children with disabilities [64] and will assess self-determination to provide insight into potential mechanisms of behaviour change.

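### Allocation is stratified by diagnosis and site, but the between-group effect sizes and intervals name neither factor, so they will be too wide if either predicts change

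*Combined protocol and SAP*

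**What the plan says.** The Randomization section states: "Group allocation occurs after baseline assessment, stratified by diagnosis and recruitment site". Under Secondary outcomes measures, the list of activity, diet, psychosocial, body composition and family measures is introduced with "Between group change will be examined using the following measures". In Data Analyses, the secondary objective is to be met by Cohen's d on the change from before to after the intervention, with "confidence intervals both within and between groups". No regression model, covariate or stratum term is named there or elsewhere.

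Diagnosis and site do appear in Data Analyses. Outcomes are to be compared between sites and disabilities under the primary objective, and by disability, functional mobility, gender and age under the secondary objective. These are separate descriptive comparisons and do not enter the contrast between arms.

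The goal measures fall outside the point: "Issue identification and goal attainment measures are administered to SFC-Peds participants only".

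**The concern.** Stratified allocation keeps the arms nearly balanced on diagnosis and site, so those factors contribute little to the real error of the arm difference. A plain two-sample interval still puts their variation into the standard error. When the factors predict change, the interval is then wider than the design allows and covers more often than its stated level.

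Two things are at stake. With 15 children per arm the half-width is already about 0.75 SD, so avoidable width matters when judging whether a measure responds to coaching. The Sample size section also intends the variance estimates from this study to feed the full trial's power calculation. If that trial adjusts for its strata, a variance that ignores them would overstate the number of children it needs.

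**Working it through.** **Inputs from the document.** Two arms of 15 (Design); 15 children with spina bifida and 15 with cerebral palsy (Recruitment); two stratification factors, with two diagnoses and two sites, so four cells (Randomization); a completion criterion of 85%, and 0.85 × 30 = 25.5, about 26 children (feasibility criteria).

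**Assumptions not in the document.** Site split 20/10, giving cells of 10/5/10/5 (15/15 was also tried); blocks of 4; 95% level; equal contribution of the two factors; and R², the share of change-score variance explained by diagnosis and site, varied from 0 to 30%.

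**The plan's own figure.** The Sample size section gives power 0.80 for an effect of 0.55 with 15 children at p < 0.10. One-sided: Φ(0.55 × √15 − 1.282) = Φ(0.848) = 0.802, or 0.784 with the noncentral t. It reproduces as a one-sided test; two-sided it gives 0.686 (z). It concerns goal attainment within the coached arm, so stratification does not bear on it.

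**Width of the between-group interval.** In units of the SD of change, the half-width is

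h = t(0.975, df) × √(4/N) × √(1 − R²),

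with df = N − 2 and the last factor set to 1 when unadjusted, and df = N − 4 with diagnosis and site as main effects.

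For N = 30, unadjusted: 2.0484 × 0.3651 = 0.748. Adjusted at R² = 0: 2.0555 × 0.3651 = 0.751, then multiplied by √(1 − R²). At 15%, for example, 0.751 × 0.922 = 0.692.

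The simulated columns come from repeated runs with stratified permuted blocks and cells of 10/5/10/5:

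| R² | Adjusted half-width (formula) | Ratio to 0.748 | Simulated ratio | Simulated coverage, unadjusted 95% interval |
|---|---|---|---|---|
| 0% | 0.751 | 1.003 | 1.008–1.009 | 95.0–95.3% |
| 5% | 0.732 | 0.978 | 0.981 | 95.4–95.5% |
| 15% | 0.692 | 0.925 | 0.925–0.926 | 96.1–96.3% |
| 25% | 0.650 | 0.869 | 0.865–0.866 | 96.9–97.2% |

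In simulations at R² of 0, 5, 10, 20 and 30%, with both site splits and N = 30, adjusted intervals covered 94.6–95.5%. The even site split gave the same pattern.

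**Break-even.** Adjustment starts to pay when R² exceeds 1 − (2.0484/2.0555)² = 0.7% at N = 30.

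**With dropout to 26.** By formula the unadjusted half-width is 0.810 and the adjusted one at R² = 0 is 0.813. In simulation, where dropout also disturbs the balance, adjustment at R² = 0 widened the interval by 1.2–1.7%.

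**Effect on d.** If d is standardized by the model's residual SD, it is inflated by 1/√(1 − R²): 1/√0.85 = 1.085, about 8% at 15%. In d units the interval then does not narrow; the simulated ratio stays near 1.009 at every R² in the table. Standardizing by the unadjusted SD keeps the narrowing (0.93 at 15%).

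**Effect on the full trial.** If that trial adjusts for its strata but is sized on an unadjusted variance, its sample size is inflated by 1/(1 − R²): 1.05, 1.18 and 1.33 at 5%, 15% and 25%.

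**The case against.** The strongest reply is that nothing shows the factors matter for the quantity analysed. The plan analyses pre-post differences, and differencing already removes stable differences in level between diagnoses and between sites. R² for change could be close to zero, in which case adjustment gains nothing and costs a little. This stands, and it is why the size is given as a range that includes zero.

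A reader might infer that the plan expects outcomes to differ by diagnosis and site. It does not say so: it undertakes to find out whether such differences exist. A reader might also infer that the plan has declared its intervals unadjusted. It is silent; adjustment is simply not specified, and a plain Cohen's d is the natural reading of that silence.

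The consequence is also limited. The plan disclaims inferential statistics, none of its feasibility success criteria uses a between-group interval, and any error is conservative. Still, the plan commits to confidence intervals as a means of establishing responsiveness, so how they are formed should be stated before the data are seen.

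**Conclusion.** The point holds conditionally. The analysis names neither stratification factor, and if diagnosis or site predicts change, the unadjusted between-group intervals will be too wide. Under the stated assumptions on cell sizes and blocks, adjustment makes the interval for the mean difference about 1% wider at R² = 0 and about 2%, 7% and 13% narrower at 5%, 15% and 25%. Unadjusted coverage rises to about 97% at the top of that range.

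It would go too far to say that the intervals are wider than they should be, because the documents give no R² for any measure. It would also be wrong to extend the point to the goal measures, which have no between-group interval, or to the feasibility conclusions. This is a cheap improvement that changes no planned conclusion. Its main value is in settling the analysis in advance and in the variance handed to the full trial.

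**What to change.** In Data Analyses, secondary objective, state that each between-group difference in change and its confidence interval come from a linear model with arm, diagnosis and site as terms. State also that Cohen's d divides this adjusted difference and its limits by the unadjusted pooled SD, not the model's residual SD, so that d is not inflated.

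The cost is one sentence, two degrees of freedom and no new data. If the factors explain nothing, intervals are up to about 1.7% wider at 85% retention.
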